5.4 Management of Strabismus

Strabismus surgery is not allowed in the first 9 weeks of the study. Strabismus surgery is allowed at the investigator’s discretion following Visit A (9-week exam), although it is *strongly* preferred that surgery be delayed until after the 18-week outcome exam. Any surgeries performed during the study will be recorded in the comment section of the Follow-up Examination Form.

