6.1 Data Analysis

The study is evaluating 2 mechanisms by which strabismic amblyopia (with and without anisometropia) may be successfully treated by spectacle correction alone:

1. Correcting small amounts of blur (including small amounts of anisometropia), with a resultant focused foveal image, may be beneficial in strabismic and combined-mechanism amblyopia (even if the amblyopic eye is not fixing or when there is no reduction in the angle of deviation).
2. Correcting moderate amounts of hyperopia might reduce the magnitude of the strabismus, which may be beneficial to the amblyopic eye.

Patients will be classified into one of three groups based on the proposed mechanism of improvement:

1. Potentially improved because of the clear image hypothesis (amblyopic eye $\geq 1.00D$ astigmatism and/or $\geq 1.00D$ spherical equivalent anisometropia with no change in angle size at distance and near). A change in angle is defined as a reduction of 10Δ or more.
2. Potentially improved because of a reduced angle of strabismus (reduction of 10Δ or more at either distance or near)
3. Combination of improved image clarity and reduced angle size

Separate analyses will be conducted within these mechanistic subgroups. Patients dropped from the study before the 18-week outcome exam or who have had strabismus surgery before the 18-week outcome exam will not be included in the analysis.

For groups 2 and 3 above, an exploratory analysis will be performed based on change in strabismic angle size during the study. This will be defined as the change in magnitude from baseline to best alignment in order to categorize patients as:

- Change from heterotropia of $>10\Delta$ to a microtropia ($\leq 10\Delta$) or orthotropia at either distance or near
- Reduction of 10Δ or more at either distance or near
- Reduction of less than 10Δ or an increase in magnitude of deviation

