6.1.1 Visual Acuity

Within each mechanistic subgroup, the proportion of patients with a 2 or more line improvement in amblyopic eye visual acuity will be calculated and an exact 95% confidence interval will be computed. A point estimate and 95% confidence interval for the mean lines of improvement in amblyopic eye visual acuity from baseline to 18 weeks will also be calculated. For each patient, the maximum acuity (at 18 weeks or after) and the visit at which this occurred will be determined. Analysis of acuity at this last visit will parallel the analysis done on visual acuity at 18-week outcome examination.

598 In the AT55 spectacle phase,⁷ the 23 patients with amblyopia cause defined as strabismus alone
 599 improved an average of 2.0 lines (SD = 1.5), with 74% improving 2 or more lines. The 42 patients
 600 with cause defined as combined-mechanism improved an average of 2.5 lines (SD = 2.0), with 64%
 601 improving 2 or more lines.

602
 603 **6.1.2 Factors Associated with Improvement in Visual Acuity**
 604 Exploratory analysis will evaluate whether patient factors such as magnitude of refractive error,
 605 baseline visual acuity, magnitude of anisometropia, stereoacuity, and change in magnitude of ocular
 606 deviation are associated with visual acuity improvement in the amblyopic eye.

607
 608 **6.1.3 Stereopsis and Ocular Alignment**
 609 To evaluate whether spectacle correction alone improves stereopsis and ocular alignment in patients
 610 not having surgery for strabismus, frequency distributions and cross-tabulations will be performed
 611 for the following:

- 612
- 613 • Stereoacuity as measured by the Randot Preschool Stereoacuity Test at the time of best
 614 amblyopic eye visual acuity compared with the stereoacuity at baseline with correction.
- 615 • Ocular alignment prior to spectacle wear compared with alignment after initial spectacle
 616 wear.
- 617 • Ocular alignment at the time of best amblyopic eye visual acuity compared with the
 618 alignment at baseline.

619
 620 **6.2 Sample Size**

621 Up to 150 patients will be enrolled. Recruitment may be discontinued if this goal is not reached
 622 within two years.

623
 624 Based upon recruitment data from AT55, it is estimated that 2 years of recruitment will result in the
 625 enrollment of 150 patients (about 6 per month) with amblyopia caused by strabismus (alone or with
 626 anisometropia), all of whom have had no prior treatment (including spectacles) for amblyopia.

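### In the exploratory angle analysis, best alignment may be a post-operative reading, because only surgery before the 18-week exam is excluded

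*Protocol*

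**What the plan says.** Section 6.1 of the protocol names two mechanisms by which spectacles might help. The second is the one at issue: "Correcting moderate amounts of hyperopia might reduce the magnitude of the strabismus, which may be beneficial to the amblyopic eye". For groups 2 and 3, "an exploratory analysis will be performed based on change in strabismic angle size during the study", and the next sentence fixes the measure: "This will be defined as the change in magnitude from baseline to best alignment in order to categorize patients as" one of three classes. The best class is a fall from more than 10Δ to 10Δ or less, at distance or near. The others are a reduction of at least 10Δ, and anything less or an increase.

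The exclusion in the same section names children dropped before the 18-week exam and those "who have had strabismus surgery before the 18-week outcome exam will not be included in the analysis". It says nothing about later operations.

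Section 5.4 states that "Strabismus surgery is allowed at the investigator’s discretion following Visit A (9-week exam"), adds that it is strongly "preferred that surgery be delayed until after the 18-week outcome exam", and has any operation noted on the follow-up form. Under 4.3 and 4.5, children whose acuity gained at least one line since the preceding study visit return every 9 weeks, with alignment measured each time. Section 6.1.3, which asks whether spectacles alone improve stereopsis and alignment, is confined to patients "not having surgery for strabismus, frequency distributions and cross-tabulations will be performed".

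**The concern.** The angle categories are there to examine mechanism 2, so a fall in angle is meant to be read as an effect of spectacles. Surgery acts directly on the angle. If a post-operative reading may serve as best alignment, a surgical result can enter the most favourable category under a spectacle label.

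The exclusion stops at 18 weeks and the angle window does not. The stated preference in 5.4 places surgery in the stretch that the exclusion leaves open.

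Any error would also lean one way. Visits after Visit B occur only in children who gained at least one line between Visit A and Visit B. A child reclassified by later surgery is therefore drawn from those with a recent acuity gain, which favours an apparent link between a smaller angle and better acuity. The change-in-deviation factor in 6.1.2 would carry the same problem if it uses the same definition.

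**Working it through.** **Rules side by side**

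| Element | Period or population | Section |
|---|---|---|
| Surgery exclusion | before the 18-week exam only | 6.1 |
| Angle change | whole study, baseline to best | 6.1 |
| Surgery allowed | after Visit A; preferred after 18 weeks | 5.4 |
| Alignment measured | every study visit, including those after 18 weeks | 4.3, 4.5 |
| Alignment tables | patients without surgery | 6.1.3 |

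As written, a child in group 2 or 3 with more than 10Δ remaining, still improving at Visit B, operated on afterwards and straight at the next 9-week exam meets the definition of the best category. Nothing in 6.1 removes that reading.

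**Number of children exposed**

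The plan's own figures reproduce: 150 × 0.90 = 135 for analysis, and half of 135 is 67.5, the 68 in its 50% column.

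The protocol gives no rate of surgery after Visit B. Assumptions, for scale only:
- groups 2 and 3 together: 68 children
- followed past Visit B: 30% to 50%
- of those, operated on and examined again: 10% to 20%
- already in the best category through spectacles: 30%, the same in operated children

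Operated children: 68 × 0.30 × 0.10 = 2.0 to 68 × 0.50 × 0.20 = 6.8.

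Only those not already in the best category can be moved into it: 2.04 × 0.70 = 1.4 to 6.8 × 0.70 = 4.8. That is about 1 to 5 children, or 2% to 7% of 68. Against a true best category of 0.30 × 68 = 20.4, the inflation is 1.43/20.4 = 7% to 4.76/20.4 = 23%.

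**Spurious link with acuity, illustrated**

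Assume no true link between angle and acuity, a gain to Visit A with mean 1.7 and SD 1.5 lines, and a gain from A to B with mean 0.6 and SD 1.0. Follow-up continues if the A-to-B gain rounds to at least one line.

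- Share continuing: P(gain ≥ 0.5) = Φ(0.1) = 0.54.
- Their excess over the average gain: φ(0.1)/Φ(0.1) = 0.397/0.540 = 0.735 line.
- With 10% operated, the share of all children moved is 0.70 × 0.54 × 0.10 = 0.0378. The difference between the best category and the rest is 0.0378 × 0.735 × (1/0.3378 + 1/0.6622) = 0.12 line.
- With 20% operated, the share moved is 0.0756. The difference is 0.0756 × 0.735 × (1/0.3756 + 1/0.6244) = 0.24 line.

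For comparison, the SD of total gain is √(1.5² + 1.0²) = 1.80. The 95% half-width for a contrast of 20.4 with 47.6 children is 1.96 × 1.80 × √(1/20.4 + 1/47.6) = 0.93 line. The distortion is about an eighth to a quarter of that. The 54% continuing is above the 30-50% assumed for the count, and stopping at resolution is ignored, so these values sit towards the upper end.

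**The case against.** The strongest objection comes from 4.1 and 4.7. Active treatment of any kind ends follow-up, and starting additional treatment after 18 weeks discontinues the patient. If surgery counts as additional treatment, no post-operative angle is ever recorded. The text points the other way. The examples in 4.1 and 4.4 are patching, atropine, filters and vision therapy. Section 5.4 permits surgery and has it recorded on the follow-up form. Section 6.1 lists surgery separately from being dropped. Still, 4.7 and 5.4 leave the matter open. A reader might infer that surgical realignment will be counted as a spectacle effect; the documents support only that it could be.

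A reader might also infer that 6.1 and 6.1.3 follow opposite rules. They do not: 6.1 is silent on surgery after 18 weeks and nowhere directs that operated children be included. The direct question about spectacles and alignment, in 6.1.3, is already protected.

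The exposed set is narrow, and this stands. The child must be in group 2 or 3, remain above 10Δ at both distance and near, gain a line from Visit A to B without resolving, be operated on while still in follow-up, and attend a later study exam. A child classed as stable at Visit B finishes the study, so later surgery never reaches the data.

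It is also fair that the analysis is exploratory and that Chapter 6 calls itself a framework to be superseded by a detailed plan. But the definition and the exclusion are both stated here, and their periods do not match. If carried forward unchanged, the gap goes with them.

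**Conclusion.** The point holds as a gap between two stated rules. Angle change runs over the whole study, the surgery exclusion ends at 18 weeks, and a post-operative alignment could be taken as best alignment in a child still improving at Visit B. The size is unknown because no surgery rate is given. About 1 to 5 of 68 children is an illustration that rests wholly on the assumed rates, and the distortion of the acuity contrast is small beside its sampling error.

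Two stronger conclusions should not be drawn. First, the 18-week acuity results are not at risk, since surgery after that exam cannot alter them; the effect is confined to an exploratory classification and, if defined alike, one factor in 6.1.2. Second, not every reclassified child need have improved from baseline. Continuation requires a one-line gain from Visit A to B, and a child who lost a line by Visit A and regained it would also continue.

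**What to change.** In 6.1, define best alignment as the best alignment measured through spectacles at a study visit before any strabismus surgery, so that angle readings are censored at the operation. Use the same angle for the change-in-deviation factor in 6.1.2, and report how many children were censored.

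Separately, reconcile 4.7 with 5.4 so that the protocol says whether strabismus surgery counts as additional treatment that ends follow-up. No view is taken here on which it should be; the censored definition works either way.

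The cost is a sentence or two. Operations are already recorded on the Follow-up Examination Form, although in its comment section, so they must be extracted from there. A few late angle readings are lost. No visit or procedure changes.

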6.1.1 Visual Acuity

Within each mechanistic subgroup, the proportion of patients with a 2 or more line improvement in amblyopic eye visual acuity will be calculated and an exact 95% confidence interval will be computed. A point estimate and 95% confidence interval for the mean lines of improvement in amblyopic eye visual acuity from baseline to 18 weeks will also be calculated. For each patient, the maximum acuity (at 18 weeks or after) and the visit at which this occurred will be determined. Analysis of acuity at this last visit will parallel the analysis done on visual acuity at 18-week outcome examination.

598 In the AT55 spectacle phase,⁷ the 23 patients with amblyopia cause defined as strabismus alone
 599 improved an average of 2.0 lines (SD = 1.5), with 74% improving 2 or more lines. The 42 patients
 600 with cause defined as combined-mechanism improved an average of 2.5 lines (SD = 2.0), with 64%
 601 improving 2 or more lines.

602
 603 **6.1.2 Factors Associated with Improvement in Visual Acuity**
 604 Exploratory analysis will evaluate whether patient factors such as magnitude of refractive error,
 605 baseline visual acuity, magnitude of anisometropia, stereoacuity, and change in magnitude of ocular
 606 deviation are associated with visual acuity improvement in the amblyopic eye.

607
 608 **6.1.3 Stereopsis and Ocular Alignment**
 609 To evaluate whether spectacle correction alone improves stereopsis and ocular alignment in patients
 610 not having surgery for strabismus, frequency distributions and cross-tabulations will be performed
 611 for the following:

- 612
- 613 • Stereoacuity as measured by the Randot Preschool Stereoacuity Test at the time of best
 614 amblyopic eye visual acuity compared with the stereoacuity at baseline with correction.
- 615 • Ocular alignment prior to spectacle wear compared with alignment after initial spectacle
 616 wear.
- 617 • Ocular alignment at the time of best amblyopic eye visual acuity compared with the
 618 alignment at baseline.

619
 620 **6.2 Sample Size**

621 Up to 150 patients will be enrolled. Recruitment may be discontinued if this goal is not reached
 622 within two years.

623
 624 Based upon recruitment data from AT55, it is estimated that 2 years of recruitment will result in the
 625 enrollment of 150 patients (about 6 per month) with amblyopia caused by strabismus (alone or with
 626 anisometropia), all of whom have had no prior treatment (including spectacles) for amblyopia.
 627 Assuming 90% of enrolled patients complete the study, we may expect to have 135 patients for
 628 analysis.

629
 630 The tables below estimate the levels of expected precision with sample sizes of varying arbitrarily
 631 chosen subgroup proportions:

632
 633 **Half-width of 95% Confidence Intervals for Mean Amblyopic Eye Improvement**

Amount of Variation in Lines of Improvement (SD)	Subgroup % of patients (N=135 patients overall)		
	25% N=34	50% N=68	75% N=102
	half-width of 95% confidence interval on mean improvement		
SD = 1.0 lines	0.3	0.2	0.2
SD = 1.5 lines	0.5	0.4	0.3
SD = 2.0 lines	0.7	0.5	0.4
SD = 2.5 lines	0.8	0.6	0.5

634
635
636

**Half-width of 95% Confidence Intervals
for Proportion of Patients with 2 or More Lines Improvement in the Amblyopic Eye**

	Subgroup % of patients (N=135 patients overall)		
Proportion of Patients with 2 or More Lines Improvement	25% N=34	50% N=68	75% N=102
	half-width of 95% confidence interval on proportion		
.40	0.17	0.12	0.10
.30	0.15	0.11	0.09
.20	0.13	0.10	0.08
.10	0.10	0.07	0.06

637

CHAPTER 7: REFERENCES

- 638
639
- 640 1. Pediatric Eye Disease Investigator Group. Treatment of anisometropic amblyopia in children
641 with refractive correction. *Ophthalmology* 2006;113:895-903.
- 642 2. Kivlin JD, Flynn JT. Therapy of Anisometropic Amblyopia. *Journal of Pediatric*
643 *Ophthalmology and Strabismus* 1981;18:47-56.
- 644 3. Clarke WN, Noel LP. Prognostic indicators for avoiding occlusion therapy in anisometropic
645 amblyopia. *American Orthoptic Journal* 1990;40:57-63.
- 646 4. Moseley MJ, Fielder AR, Irwin M, Jones HS, Auld RJ. Effectiveness of occlusion therapy in
647 ametropic amblyopia: a pilot study. *Br J Ophthalmol* 1997;81:956-61.
- 648 5. Krumholtz I, FitzGerald D. Efficacy of treatment modalities in refractive amblyopia. *J Am*
649 *Optom Assoc* 1999;70:399-404.
- 650 6. Stewart CE, Moseley MJ, Fielder AR, Stephens DA, MOTAS Cooperative. Refractive
651 adaptation in amblyopia: quantification of effect and implications for practice. *Br J*
652 *Ophthalmol* 2004;88:1552-6.
- 653 7. Cotter S, Edwards A, Arnold R, Astle W, Barnhardt C, RW B, et al. Treatment of
654 strabismic amblyopia with refractive correction. *Am J Ophthalmol* 2007;143:1060-1063.
- 655

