257 1. Ocular Alignment Testing: Ocular alignment at distance and near will be assessed with the
258 cover/uncover test to determine if a tropia is present; if present, it must be determined
259 whether the frequency is constant or intermittent.

- 260 • Strabismic deviations will be measured first with the Simultaneous Prism and Cover
261 Test (SPCT) and then by the Alternate Prism and Cover Test (APCT) in primary
262 position at distance and near using the methods as outlined in the ATS Testing
263 Procedures Manual. The SPCT measurements should always be performed before
264 the APCT measurements.
- 265 • Testing must be performed prior to cycloplegia.
- 266 • Measurements made using the Krimsky test are NOT allowed.
- 267 • Testing must be performed no more than 7 days prior to enrollment.

268
269 2. Visual Acuity Testing: Visual acuity testing will be done by a certified examiner using the
270 ATS single-surround HOTV letter protocol on the Electronic Visual Acuity Tester. The
271 protocol for conducting visual acuity testing is described in the ATS Testing Procedures
272 Manual. Aspects of the testing protocol that are specific to this study are:

- 273 1. Testing is performed with the optimal refractive correction (*section 2.5*) as
274 determined from a cycloplegic refraction completed no more than 2 months prior.
- 275 2. Testing can be performed without cycloplegia or after cycloplegia when the child is
276 sufficiently attentive for this to be accomplished (*although it is preferable that*
277 *testing be done without cycloplegia*).
- 278 3. Testing must be performed no more than 7 days prior to enrollment.

279 If the patient is uncooperative because of resistance to wearing trial frames or using a
280 phoropter, he/she should be given a 15-minute break before attempting to retest. If the
281 patient is still uncooperative and visual acuity is not attainable, the child can not be enrolled
282 in the study at this time. However, the patient may be retested on a different day provided
283 no spectacles are worn in the interim.

284 3. Additional Clinical Testing:

- 285 1. Ocular examination as per investigator's clinical routine to rule out a cause for
286 reduced visual acuity other than amblyopia
 - 287 • If performed within prior 2 months, do not need to repeat at time of enrollment
- 288 2. Cycloplegic refraction using cyclopentolate 1% as per investigator's usual routine

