3.1 Baseline Visit

All enrolled patients will have a Baseline Visit within 30 days after the Screening Visit. At this Baseline Visit, the new spectacles with the optimal refractive correction based on the cycloplegic refraction will be placed on the child for the first time.

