3.2 Procedures at the Baseline Visit

1. The spectacles prescription should be verified with a lensometer.
 - Sphere and cylinder power must be within 0.25 D of the prescribed correction. Cylinder axis must be within 6 degrees of the axis in the spectacles when cylinder power is >1.00D. If these criteria are not met, the spectacles must be re-made and the patient will return at a later date for the Baseline Visit.
2. The patient should wear the new spectacles for 10 to 30 minutes before the testing in #3-5 below is performed.
3. Visual acuity testing will be done without cycloplegia by a certified examiner using the ATS single-surround HOTV letter protocol on the Electronic Visual Acuity Tester. Both the amblyopic and sound eyes must be retested on the same day with a -1.00D lens over the new spectacles (thus decreasing the chance that any persistent accommodative tone will compromise distance visual acuity and making it more likely that best-corrected visual acuity is measured). Baseline visual acuity is considered the better of the two acuity measures. The protocol for conducting the visual acuity testing is described in the ATS Testing Procedures Manual.
4. Ocular alignment with the cover/uncover test, SPCT, and APCT (*section 2.3.2*) at distance and near is evaluated through the new spectacles.
5. Stereoacuity with the Titmus fly and Randot Preschool Stereoacuity tests

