4.3 Testing Procedures

1. Visual acuity testing at all follow-up exams will be done without cycloplegia by a certified examiner using the ATS single-surround HOTV letter protocol on the Electronic Visual Acuity Tester.
 - Amblyopic eye visual acuity must also be retested with a -1.00D lens over the optimal refraction (to account for possible persistent accommodative tone).
 - If the sound eye visual acuity is reduced 1 or more lines from the previous visit, the sound eye must also be retested with a -1.00D lens over the optimal spectacle correction.
 - Follow-up visual acuity is considered the better of the two acuity measures (with and without the -1.00D lens). The protocol for conducting the visual acuity testing is described in the ATS Testing Procedures Manual.
 - For Visit B (18-week outcome exam) and all subsequent exams, if the better of the two visual acuities (with and without the -1.00D lens over spectacles) is not at least 1 line better than the visual acuity from the previous study visit, the study ends for this patient. If the better of the two visual acuities (with and without the -1.00D lens) is at least 1 line better than the visual acuity at the previous study visit, study follow-up continues.
2. Detection of strabismus at distance and near by cover/uncover testing, with measurement of any strabismus using the Simultaneous Prism and Cover Test (SPCT) and the Alternate Prism and Cover Test (APCT) (*section 2.3.2*) is performed through the optimal refractive correction. The SPCT should be performed before the APCT (*section 2.3.2*).
 - If the spectacles are bifocals, ocular alignment at near should be tested through the bifocal portion of the lenses. If necessary, the bifocals should be raised to ensure that the patient is viewing the near target in primary position (not down gaze) while looking through the bifocal lenses.
3. Stereoacuity with the Titmus Fly and Randot Preschool Stereoacuity tests

449 **4.4 Changes in Treatment Prior to the 18-week Outcome Visit**

- 450 • Amblyopia treatment in addition to spectacles (e.g., patching, atropine, vision therapy,
451 filters) is NOT allowed prior to the 18-week outcome exam.
- 452 • If the investigator determines that a spectacle change is required after the child has worn the
453 glasses initially prescribed, spectacles may be changed prior to the 18-week outcome exam.
454 Bifocals may be prescribed at any visit after the Baseline Visit if the esotropia at near

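### Baseline acuity is tested as a factor for an improvement score that starts from the same measurement, so test error alone makes worse baseline acuity appear to go with more gain

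*Protocol*

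**What the plan says.** Section 6.1.2 is short: "Exploratory analysis will evaluate whether patient factors such as magnitude of refractive error", followed by "baseline visual acuity, magnitude of anisometropia, stereoacuity, and change in magnitude of ocular" deviation, are associated with improvement in the amblyopic eye. No model is named.

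Section 6.1.1 defines the score through the "mean lines of improvement in amblyopic eye visual acuity from baseline to 18 weeks". It also plans a parallel analysis of the maximum acuity at 18 weeks or later. Both scores start at Baseline.

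Section 3.2, item 3, sets the starting value: "Baseline visual acuity is considered the better of the two acuity measures", meaning the tests with and without the -1.00D lens on the same day. Section 4.3 scores later visits likewise: "Follow-up visual acuity is considered the better of the two acuity measures".

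A separate, earlier acuity exists. For Screening, section 2.3.2 states "Visual acuity testing will be done by a certified examiner using the" same HOTV protocol, and "Testing is performed with the optimal refractive correction". Section 3.1 places the second measurement later: "All enrolled patients will have a Baseline Visit within 30 days after the Screening Visit". Section 3.3.2 already compares the two acuities to detect refraction errors, but chapter 6 gives Screening acuity no role.

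**The concern.** Improvement is Baseline acuity minus follow-up acuity. A child who tests one line too badly at Baseline has both a worse recorded baseline and one extra line of recorded gain. Across children, this produces a positive association even if true gain does not depend on true severity.

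The study has no control group, so nothing in the design separates this artefact from a real effect. At stake is how one exploratory result is read. A finding that children with worse acuity gain more from spectacles could be partly or wholly measurement error.

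**Working it through.** **Inputs from the protocol.** Enrolment is up to 150 with 90% completing: 150 × 0.90 = 135, which reproduces the stated number for analysis (section 6.2). Expected gain is a mean of 2.0 lines (SD 1.5) for strabismus alone and 2.5 lines (SD 2.0) for combined mechanism (section 6.1.1). The protocol states no figure for the baseline association itself.

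**Assumptions, not in the protocol.** Test error SD is 0.5 to 1.0 line, true baseline SD is 1.5 to 2.5 lines, errors at different visits are independent, and true gain is unrelated to true baseline.

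**Algebra.** Count lines so that higher is worse. Let B = T + e (Baseline), F = T − g + f (follow-up) and I = B − F = g + e − f (improvement). If g is unrelated to T, Cov(I, B) = Var(e), so

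- slope of I on B = σe² / (σT² + σe²);
- correlation = σe² / (SD of B × SD of I).

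With σT = 2:

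- σe = 0.5: 0.25/4.25 = 0.06
- σe = 0.7: 0.49/4.49 = 0.11
- σe = 1.0: 1.00/5.00 = 0.20

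With the protocol's SDs of change, the correlation runs from 0.25/(2.06 × 2.0) = 0.06 to 1.00/(2.24 × 1.5) = 0.30. By Fisher's z with n = 135, the chance of a nominal p < 0.05 with no true relation is 11% to 94%. Over σT from 1.5 to 2.5 the slope is 0.04 to 0.31.

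**Does another model avoid it?** No. The slope of F on B is Cov(B − I, B)/Var(B) = 1 minus the slope above, so it carries the same error.

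**Adding the protocol's own rules.** A simulation used better-of-two scoring at Baseline and follow-up, whole-line rounding, and the acuity criteria at both Screening and Baseline. Recorded baseline SD was about 1.6 lines. The last column is the Baseline slope × 3.2 lines (2 × 1.6).

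| Error SD (lines) | Slope, Baseline as factor | Slope, Screening as factor | Baseline artefact across ±1 SD |
|---|---|---|---|
| 0.5 | 0.08 | −0.02 | 0.26 line |
| 0.7 | 0.12 | −0.03 | 0.38 line |
| 0.9 | 0.17 | −0.05 | 0.54 line |

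Adding a true gain independent of baseline (mean 2 lines, SD 1.3) left the slopes unchanged.

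A second simulation applied the same rules with true baseline SD 2 and error SD 0.5 to 1.0. It gave Baseline slopes of 0.07 to 0.19, nominally significant in 10% to 72% of trials of 135. With Screening as the factor the slopes were −0.02 to −0.04 and the rate was 6% to 9%. Widening true SD to 1.5 to 2.5 gave Baseline slopes of 0.05 to 0.28, against −0.02 to −0.05 for Screening.

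These significance rates are for a pooled analysis. If the factor analysis is run within the mechanistic subgroups, smaller numbers lower the rates but do not remove the bias.

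**The case against.** **The analysis is exploratory and the model is open.** Section 6.1.2 names no regression, and chapter 6 calls itself a synopsis that a detailed analysis plan will supersede. This limits the weight of the point. It does not remove it, because the protocol already names the factor and fixes the score, and the overlap follows from those two whichever of the two usual models is fitted.

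**The size is assumed.** This stands. At the low end the artefact is small. A reader might also multiply the slope by the 10 lines from 20/40 to 20/400 and infer a spurious difference of 0.8 to 1.7 lines. That range is about 6 SDs of recorded baseline (10/1.6), a contrast that describes almost no pair of enrolled children. Plus or minus 1 SD is the fairer scale.

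**Screening acuity is not a like-for-like measure.** This also stands. It is taken in trial frames or a phoropter, possibly under cycloplegia, with no stated -1.00D retest. Where the refraction proves wrong and spectacles are remade (section 3.3), it reflects a different correction. It is also an eligibility test. These facts argue against replacing Baseline acuity with it, but not against reporting it alongside.

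**Change in ocular deviation.** A reader might infer that this listed factor should go too, because it develops alongside acuity. The protocol does not support that. Section 6.1 makes a reduced angle one of the two mechanisms under study, and section 6.1.2 is about association, not only about prior predictors.

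**Conclusion.** The point holds as a minor one. The direction follows from the protocol's definitions and any non-zero test error: worse recorded baseline will go with more recorded gain. Under the stated assumptions (error SD 0.5 to 0.9 line, recorded baseline SD about 1.6 lines) the artefact is about 0.08 to 0.17 lines of gain per line, or roughly 0.3 to 0.5 line across plus or minus 1 SD.

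Three stronger readings are not supported:

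- The primary estimates are not affected by this overlap. The proportion gaining 2 or more lines and the mean gain do not use the association.
- An observed association need not be all artefact. A real one may coexist, for instance because a worse start leaves more room to improve. Only the part created by error is at issue.
- Nothing in the protocol ties section 6.1.2 to a rule about which children are offered spectacles alone.

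**What to change.** In section 6.1.2, keep baseline visual acuity and add the association of improvement (Baseline to 18 weeks) with Screening amblyopic-eye acuity. Report the two side by side. State that baseline severity will be said to predict gain only if the Screening-based estimate supports it.

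The cost is analysis wording only, since the data are already collected. The Screening estimate has two known weaknesses to state with it:

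- A true slope is attenuated by σT²/(σT² + σe²). With σT = 2 this is 4/4.25 = 0.94 at error SD 0.5 and 4/5 = 0.80 at error SD 1.0.
- Selection on acuity at both visits leaves a small opposite bias of about −0.02 to −0.05. A weakly negative or near-zero Screening slope should therefore not be read as evidence that severity does not matter.

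The differences in testing conditions between Screening and Baseline should be noted beside the result.
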